A Controlled Study of the Efficacy of Botulinum Toxin A (Botox) for the Treatment of Social Anxiety Disorder (SAD)

[name]
[name], PhD

CONTACT INFORMATION

Primary contact:
[name], [contact], [contact]

CLINICAL STUDY PROTOCOL SUMMARY

Sponsor: Dermatology and Cosmetic Surgery Associates, LLC

Investigational Treatment: Five injections of Botox will be administered at a single treatment visit.

Title of Study: A Controlled Study of the Efficacy Botox Treatment for the Treatment of Social Anxiety Disorder (SAD)

Date: 3/8/2016

Number of centers: One

Primary Objective: The objective of this proposed study is to obtain data on the efficacy of Botox in reducing symptoms of social anxiety disorder (SAD) in male and female patients between the ages of 18 and 65 years old. Efficacy will be determined by using a continuous measure of outcome, the Liebowitz Social Anxiety Scale (Primary outcome) (LSAS; Fresco et al, 2001) and dichotomous indicators of response (Primary outcome) (LSAS <50) and remission (Secondary Outcome) (LSAS <30). Subjects will be assessed using: the self-rated LSAS and the self-rated version of the BDI-I at screening, 4 weeks, and 8 weeks.

Statistical Considerations: An ANOVA with repeated measures to determine whether there are statistical differences between the interventions will be used. Because the effect size of the intervention is unknown, the power statistics required to obtain significant differences between placebo and Botox cannot be calculated.

Number of Patients Planned: Up to 100 subjects will be screened in order to enroll 30.

Diagnosis and Criteria for Inclusion: Patients will be included in this study if they meet all of the following criteria:

Written informed consent is obtained;
They are a 18 to 65 years old;

A primary diagnosis for SAD as diagnosed by the MINI, and their current episode must be at least one month in length; A total score on the LSAS of 60 or greater
Women of childbearing potential (WOCBP) are on an acceptable form of birth control and are not pregnant or lactating;
They are judged by the investigator to have the capacity to understand the nature of the study;
They are willing to comply with all the requirements of the study.
They are considered by the investigator to be likely to adhere to the protocol.

Criteria for Exclusion: Patients will be excluded from this study if they meet any of the following criteria:

They have ever been treated with botulinum toxin A ;

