They have another Axis I disorder as a principal diagnosis in the 6 months prior to screening;
They have a history of substance abuse or dependency in the 2 months prior to screening;
Pregnant women, lactating women, and women of childbearing potential not using medically accepted forms of contraception;
Patients with current or recent suicidality;
Scoring 10 or greater on the BDI
Scoring 2 or greater on the suicide question of the BDI
Psychotic disorders, bipolar disorder;
They are considered to be at a significant risk of committing homicide;
They have an unstable medical condition;
Women of childbearing potential (WOCBP) who are pregnant or are considering becoming pregnant during the length of the study;
They are regarded, for any reason by the principal investigator as being an unsuitable candidate for the protocol.
There has been a change in their medication or psychotherapy treatment regimen in the month preceding screening;

Mode of Administration: Patients will be randomly assigned to the active group or control group in a 1:1 ratio. Patients in the control group will be injected with a saline solution. Patients in the active group will receive 40 units of Botox (females) or 50 units (males). For females, 8 units will be injected into the procerus and 8 units into both the right and left medial and lateral corrugators. For males, 10 units will be injected into each location.

Method of Blinding: This will be a double-blind study. The clinician administering the injections will be blinded. After the initial visit, to help maintain the blind, all data will be collected via a web portal with online questionnaire assessments.

Duration of Treatment: The study will be divided into three phases: screening and enrollment, treatment, and follow-up. Patients who meet all criteria will be randomized at the screening visit. The follow-up phase will last eight (8) weeks after the investigational product is administered. Patients will be instructed to complete the LSAS and BDI online at week 4 and 8.

General Design and Methodology: Prior to screening, potential participants will fill out the LSAS and BDI online in order to determine initial eligibility. Those who meet the criteria will be

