However, adverse effects are dependent upon the site of injection. No definitive serious adverse event reports of distant spread of toxin effect associated with dermatologic use of Botox for glabellar lines have been reported. Similarly, no definitive serious adverse event reports of distant spread of toxin effect associated with Botox for blepharospasm at the recommended dose or for strabismus at the labeled doses have been reported.

Hypersensitivity Reactions

Serious and/or immediate hypersensitivity reactions have been reported. These reactions include anaphylaxis, urticaria, soft tissue edema, and dyspnea. One fatal case of anaphylaxis has been

reported in which lidocaine was used as the diluent, and consequently the causal agent cannot be reliably determined.

Pre-Existing Neuromuscular Disorders

Patients with neuromuscular disorders may be at increased risk of clinically significant effects including severe dysphagia and respiratory compromise from typical doses of Botox.

Human Albumin

This product contains albumin, a derivative of human blood. Based on effective donor screening and product manufacturing processes, it carries an extremely remote risk for transmission of viral diseases. A theoretical risk for transmission of Creutzfeldt-Jakob disease (CJD) also is considered extremely remote. No cases of transmission of viral diseases or CJD have ever been identified for albumin.

PURPOSE OF THE STUDY AND STUDY OBJECTIVES

Purpose of the Study

The purpose of the study is to evaluate the efficacy of botulinum toxin A as a treatment for SAD.

Study Objectives

The primary objective of this proposed study is to obtain data on the efficacy of Botox in reducing symptoms of SAD in male and female patients between the ages of 18 and 65 years old.

Efficacy will be determined by using a continuous measure of outcome, the Self Rated Liebowitz Social Anxiety Scale (Fresco et al, 2001) and dichotomous indicators of response (LSAS < 50) and remission (LSAS < 30).

Patients will also be assessed with the self-rated version of the BDI at screening, 4 weeks, and 8 weeks.

STUDY DESIGN

The study will begin in May 15, 2016 and be completed by September 2017. Approximately 30 patients will be randomized and enrollment will be complete when that number is reached. It is estimated that up to 100 patients will have to be screened in order to randomize 30.

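### Primary response (LSAS below 50) depends strongly on screening severity, and no stratification or adjustment for screening LSAS is stated; pre-specify an adjusted comparison

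*Combined protocol and SAP*

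**What the plan says.** The Primary Objective in the Clinical Study Protocol Summary names two primary outcomes. One is "a continuous measure of outcome, the Liebowitz Social Anxiety Scale (Primary outcome"). The other is response, which appears among the "dichotomous indicators of response (Primary outcome) (LSAS <50) and remission (Secondary Outcome) (LSAS <30"). Study Objectives repeats the cut-offs: "dichotomous indicators of response (LSAS < 50) and remission (LSAS < 30"). Neither place relates response to the patient's own starting score.

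The inclusion criteria require "A total score on the LSAS of 60 or greater" and give no upper limit. On size, Study Design states: "Approximately 30 patients will be randomized and enrollment will be complete when that number is reached". On allocation, Mode of Administration states: "Patients will be randomly assigned to the active group or control group in a 1:1 ratio". With 30 patients that is about 15 per arm. Stratification by severity is not mentioned.

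Statistical Considerations names one analysis: "An ANOVA with repeated measures to determine whether there are statistical differences between the interventions will be used". It lists no covariate and no test for the binary response. It adds: "Because the effect size of the intervention is unknown, the power statistics required to obtain significant differences between placebo and Botox cannot be calculated". The documents give no LSAS mean, standard deviation or expected response rate.

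**The concern.** A fixed end score asks different things of different patients. A patient who goes from 60 to 49 is a responder; one who goes from 100 to 50, halving the score, is not. The chance of response therefore varies sharply with screening score even if treatment does the same for everyone.

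With about 15 per arm, mean severity will often differ between arms by several points. Without stratification or adjustment, that difference passes straight into the response comparison. A real benefit can be missed if the active arm happens to enter more severe, and the observed difference is hard to interpret in either direction.

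**Working it through.** **Plan's own figure.** There is nothing to reproduce. The 30 patients come without alpha, power, effect, SD or response rates.

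**1. Fall needed (no assumption except integer scores).** Points needed = screening LSAS - 49.

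| Screening | Points | Share of screening score |
|---|---|---|
| 60 | 11 | 11/60 = 18% |
| 70 | 21 | 21/70 = 30% |
| 80 | 31 | 31/80 = 39% |
| 100 | 51 | 51/100 = 51% |

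**2. Chance of response by screening score.** Assume the same normal change for everyone, with mean -15 and SD 20. Then P(response at screening s) = Φ((49.5 - s + 15)/20).
- s = 60: Φ(0.225) = 59%
- s = 80: Φ(-0.775) = 22%
- s = 100: Φ(-1.775) = 4%

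Over four assumed changes (mean/SD -10/12, -15/15, -15/20, -25/20) the ranges are 48-77%, 4-39% and 0-10%.

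**3. Size of chance imbalance (model A).** Assumptions: screening LSAS is normal, truncated to 60-144 (144 as the scale maximum is itself an assumption), with mean 77, 83 or 89 and SD about 10, 13 or 17. It is crossed with the four changes above, giving 12 scenarios of 40,000 simulated trials at 15 v 15. Change is independent of screening score.
- SD of the difference in mean screening LSAS = SD × √(2/15). This gives 10.1 × 0.365 = 3.7 points up to 16.6 × 0.365 = 6.1 points.
- A gap of more than 5 points between arms occurs in 17-41% of trials.
- Imbalance alone shifts the expected response difference by up to 8-16 percentage points (95th percentile). For scale, the total SD of the observed difference is 9-18 points.

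**4. Hiding an effect (model A, true 15-point benefit, two-sided Fisher test at 0.05; the plan names no test).**
- Power overall: 11-32%
- Active arm enters more than 5 points worse: 2-9%
- Active arm enters more than 5 points milder: 25-61%
- t-test on LSAS change, same data: 51-91%

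**5. False positives (model A, no effect).** Fisher rejects in 0.2-1.8% of trials overall, and in at most 3.4% when the active arm enters more than 5 points milder.

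**6. What drives response status (model A).** Screening score explains 11-23% of its variance and the patient's change explains 20-59%. Change is clearly ahead in 11 of 12 scenarios; in the twelfth both are about 20%.

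**7. Effect of adjusting (model B).** Assumptions: true LSAS mean 75, SD 20; visit error SD 8; screening cut at 60; saline change -12, SD 15; Botox benefit 20 points; 15 v 15.

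| Comparison | Power |
|---|---|
| LSAS below 50, unadjusted Fisher | about 27% |
| LSAS below 50, exact test stratified at screening 70, 75 or 80 | 37-38% |
| 40% fall from own screening score | about 38% |
| 50% fall from own screening score | about 28% |
| Screening-adjusted continuous LSAS | about 80% |

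Type I error of the stratified exact test is about 2%.

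**The case against.** The strongest reply is that an end-state threshold is a legitimate outcome. It asks whether patients reach a low symptom level, and a percentage fall has an arbitrary cut of its own. This stands: nothing in the documents shows that the cut-off of 50 is an error, and step 7 shows that a percentage rule gains power at 40% but not at 50%.

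It is also fair that continuous LSAS is primary and is measured at screening, week 4 and week 8. Information on severe patients is lost only from the dichotomy, and the trial does not rest on the cut-off alone. That does not settle how the response result, which is also labelled primary, should be compared. Most of the low power comes from dichotomising with 30 patients, and adjustment recovers only part of it.

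Two stronger readings are tempting. A reader might infer that response mostly measures how mild the patient was at entry. The documents give no LSAS distribution that would show this, and under the assumed ones change explains as much or more (step 6). If change regressed toward the mean, the role of screening score would be smaller still. A reader might also infer that imbalance can manufacture a significant result. Allocation is randomised 1:1, so imbalance is chance error that the test already allows for, and false positives stay below 5% even when the active arm enters milder (step 5).

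**Conclusion.** The point holds as one of precision and interpretability. That response depends strongly on screening severity follows from the entry rule and the cut-off alone: the required fall is 18% from 60 and 51% from 100. With no stratification or adjustment stated, chance imbalance adds avoidable noise, roughly 8-16 percentage points at the 95th percentile, and can cut already low power to single figures when the active arm enters worse.

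The comparison is not biased, and the cut-off is not shown to be wrong. All figures beyond the threshold arithmetic rest on assumed LSAS distributions, because the documents supply none. The direction was the same in every scenario run; the sizes would move with the real spread of screening scores and changes.

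**What to change.** Keep LSAS below 50 as the response definition. Add to Statistical Considerations a sentence that the proportions with LSAS below 50 will be compared between arms with adjustment for screening LSAS, for example by an exact test stratified at one screening score fixed before unblinding. Under model B, cuts at 70, 75 and 80 perform alike, so the exact choice matters little there. The sentence should also name the visit (week 4 or week 8) and say which pre-treatment LSAS is used, since the plan has one completed online beforehand and one at the screening visit.

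A percentage fall from the patient's own screening LSAS may be reported as a supportive measure, with the percentage fixed in advance. Replacing the cut-off of 50 is optional, because the gain depends on the percentage chosen.

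The cost is a sentence or two of analysis text and, if the supportive measure is added, one table row. No new data are needed. The one drawback is that a stratifying score must be committed to in advance.

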scheduled for an in-person screening visit. At screening, patients will sign consent and be diagnosed by means of the MINI (Sheehan et al,1998) , and will have a DSM-IV diagnosis of Social anxiety disorder (SAD). They will complete the LSAS. They will also complete the patient-rated BDI (Beck et al.,1961). Patients who meet all criteria will be randomly assigned to receive either the investigational product or placebo. Patients will be photographed, at the initial visit, at rest. The study medication or placebo will be injected within 7 days of clinical assessments into the procerus and corrugator supercilii frown muscles of each patient by a physician's assistant who is experienced in the administration of this medication. Four weeks \pm 7 days, and eight weeks \pm 7 days following the injection, each patient will complete online assessments. Patients will complete online the adverse events (AEs) and concomitant medications questionnaires will be at week 4 and 8.

Investigational New Drug (IND) Application: This study is exempt from the requirement for an IND submission based on the following criteria: Botox is lawfully marketed in the United States. There is no intent to report the findings of this trial to the FDA in support of a new indication or any significant change in the labeling of the drug. This study is not intended to support a significant change in the advertising of the prescribed drug. Compared to the current labeling of Botox, there will be no change in the route of administration, the dosage level, or any other factor that significantly increases the risk, or decreases the acceptability of the risk, associated with the use of the drug. Botox is approved for doses up to 400 units. We will use 40 or 50 units. The patient population will be different compared to the current labeling, which specifies bladder dysfunction, chronic migraine, upper limb spasticity, cervical dystonia, blepharospasm, strabismus and primary axillary hyperhidrosis. The change in population will not significantly increase the risk. All participants in the study will be medically stable adults.

BACKGROUND INFORMATION

Introduction

Investigational Treatment

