Two phase 3 randomized, multi-center, double-blind, placebo-controlled studies of identical design were conducted to evaluate Botox for use in the temporary improvement of the appearance of moderate to severe glabellar facial lines. The studies enrolled healthy adults (ages 18 to 75) with glabellar lines of at least moderate severity at maximum frown. Subjects were injected intramuscularly in five sites, 1 in the procerus muscle and 2 in each corrugator supercilii muscle, for a total dose in the active treatment groups of 20 Units. In these studies, the severity of glabellar lines was reduced for up to 120 days in the Botox group compared to the placebo group as measured both by investigator rating of glabellar line severity at maximum frown, and by subject's global assessment of change in appearance of glabellar lines. Analysis of the limited number of patients 65 years or older suggested a lower treatment-associated response compared to patients less than 65 years of age. (Botox website)

Depression

The first open label trial of Botox to the glabellar muscle complex to treat unipolar depression was published in 2006. Since that time, three randomized double blind placebo-controlled trials were conducted to assess the efficacy of Botox treatment of the glabellar muscle complex in major depression. All three studies showed a response rate of 50 to 60%, and the remission rate of approximately one-third. To date, no clinical trials of Botox have been conducted in SAD.

Social Anxiety Disorder (SAD)

Social anxiety disorder (SAD) is a common psychiatric condition marked by persistent fear and anxiety of one or more social or performance situations. The lifetime prevalence of the disorder is 12%, and leads to significant morbidity for those affected. The only FDA approved treatments for SAD have response rates of 40 to 60 %, and remission rates of 20%. Therefore, there is a real need for the development of new and effective treatments for SAD.

Patients suffering from SAD either avoid situational triggers or endure intense anxiety and distress, leading to an impaired social life in either scenario. SAD is characterized by an overactive anxiety pathway with a perceptual and cognitive bias towards threat.

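### The only efficacy analysis names no test term, visit or role for screening LSAS; adjusting the week-4 and week-8 comparison for the screening-visit LSAS is usually more precise and costs one degree of freedom

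*Combined protocol and SAP*

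**What the plan says.** The Statistical Considerations paragraph of the Clinical Study Protocol Summary gives the only efficacy analysis: "An ANOVA with repeated measures to determine whether there are statistical differences between the interventions will be used". The same paragraph says that power cannot be calculated because the effect size is unknown. Study Objectives, later in the protocol, repeats the outcomes without adding a model or a time point.

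The Primary Objective makes LSAS the continuous primary outcome and schedules "the self-rated LSAS and the self-rated version of the BDI-I at screening, 4 weeks, and 8 weeks". Duration of Treatment confirms the follow-ups: "Patients will be instructed to complete the LSAS and BDI online at week 4 and 8". Entry requires "A total score on the LSAS of 60 or greater", and the size is stated as "Up to 100 subjects will be screened in order to enroll 30", allocated 1:1.

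There are two LSAS scores before treatment. One is completed online to determine initial eligibility. The other is at the in-person screening visit, where General Design and Methodology says of patients: "They will complete the LSAS".

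**The concern.** A repeated-measures ANOVA on three visits is a family of tests, and the sentence does not choose one. At least five readings fit it or can be reached from it:

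1. Screening is one of three repeated levels and the arm main effect is tested.
2. The arm-by-time interaction is tested, with 2 degrees of freedom and no visit singled out.
3. Only weeks 4 and 8 are compared, and the baseline is unused.
4. Change from screening is compared, which is the 1-degree-of-freedom arm-by-time contrast.
5. Weeks 4 and 8 are compared with screening LSAS as covariate.

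These readings differ in what they estimate and in power. Leaving the choice open also lets the result influence which test is reported. With about 15 patients per arm and no power calculation, the plan has little precision to spare, and a baseline score that could recover some has no stated use.

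**Working it through.** **Inputs from the documents.** 30 patients randomised 1:1, so 15 per arm; LSAS at screening, week 4 and week 8; entry cut-off of 60. No alpha, SD, correlation or effect size is given, so there is no figure of the plan to reproduce.

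**Assumptions.** Two-sided 5%; no dropout; unit SD at each visit and a common correlation r = 0.3/0.5/0.7 between visits, both before the cut-off is applied. The cut-off truncates a normal baseline and leaves follow-up given baseline unchanged. The documents do not say where 60 falls in the candidate pool, so I show two positions, and no cut-off as the limiting case.

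**Dilution.** Screening precedes treatment, so an effect e at both follow-ups enters the three-visit arm effect as (0 + e + e)/3 = 2e/3.

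**CI width, same contrast (average of weeks 4 and 8).** This needs no effect size.
- Baseline variance vb: 1 with no cut-off, 0.63 with the cut-off 1 SD below the mean, 0.36 with it at the mean.
- V_adj = (1+r)/2 − r²; V_unadj = V_adj + r²·vb.
- Width ratio = (t27/t28)·√(V_adj·(27/26)/V_unadj), where 27/26 is the average cost of estimating the slope.
- Example, r = 0.5 and cut-off 1 SD below: V_adj = 0.75 − 0.25 = 0.50; V_unadj = 0.50 + 0.25 × 0.63 = 0.66; ratio = (2.052/2.048)·√(0.50 × 1.038/0.66) ≈ 0.89, so 11% narrower.

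| Position of the cut-off | CI narrower at r = 0.3/0.5/0.7 | Break-even r, average | Break-even r, one visit |
|---|---|---|---|
| 1 SD below mean | 3/11/25% | 0.19 | 0.25 |
| At mean | 1/6/17% | 0.25 | 0.32 |
| Not binding | 5/17/34% | 0.15 | 0.20 |

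Break-even is the r at which the ratio equals 1. For one visit, V_adj = 1 − r². At r = 0.3 with the cut-off at the mean, an adjusted week-8 interval is about 0.3% wider than the unadjusted one.

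**Illustrative power.** Assumed effect: 0.8 follow-up SD at both visits. Simulated, 40,000 trials per setting, r = 0.3/0.5/0.7.

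| Test | Cut-off 1 SD below mean | Cut-off at mean |
|---|---|---|
| Three-visit arm effect | 56/47/40% | 63/55/46% |
| Arm-by-time, 2 df | 47/58/76% | 50/57/69% |
| Weeks 4 and 8, unadjusted | 76/70/65% | 76/71/67% |
| Weeks 4 and 8, adjusted | 78/80/88% | 77/76/82% |
| Gain over unadjusted | 2/10/23 points | 1/5/15 points |
| Gain over change from screening | 17/10/4 points | 10/5/2 points |

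**Choosing the test late.** In simulated trials with no effect, each test alone rejects in 4.8–5.3%. At least one of readings 1–3 has p<0.05 in 10.4–11.6%, and in about 13% if change from screening is added.

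**The case against.** The strongest reply is that repeated-measures ANOVA is a recognised method, that any version fixed in advance is valid, and that the choice of contrast is partly preference. Much of that stands. Each test holds about 5% on its own. The average of weeks 4 and 8 is not always best: if the effect appears at one visit only (no cut-off), arm-by-time has 45/59/82% power against 28/31/41% for the adjusted average. The background reports for the cosmetic use that "the severity of glabellar lines was reduced for up to 120 days in the Botox group compared to the placebo group", which spans both visits, but the documents give no time course for anxiety. The plan should therefore name a contrast; the documents do not dictate which.

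A second reply is that the baseline is less settled than it looks. Besides the earlier online LSAS, the Study Design account of the screening visit lists the interview, medication review and pregnancy test but no LSAS. General Design and Methodology does place one there, and the Primary Objective schedules one at screening, so the covariate is planned. The text still has to say which score it is.

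Three stronger readings are tempting and unsupported:
- **That the plan inflates type I error.** The 11% arises only if the test is chosen after seeing the data, and nothing in the documents says that it will be.
- **That the planned test is the diluted one.** The sentence does not say so.
- **That adjustment gains up to 30 points, or helps at any correlation above 0.15 to 0.20.** Those figures (93 against 63% power at r = 0.7, and the break-evens) require that the entry cut-off does not bind.

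**Conclusion.** The omission is confirmed: no section names the test term, the visit or the role of screening LSAS. It should be fixed, although it does not make the stated method invalid.

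Adjustment is usually, not always, more precise for the same contrast. With the cut-off in place at the two positions shown, the interval narrows by 1 to 25%, and power for a 0.8 SD effect rises by about 1 to 23 points over ignoring the baseline. That gain is small at low correlation. Against change from screening the pattern reverses: the gain is largest at low correlation and small at high. All of these sizes rest on assumed correlations, distribution and cut-off position, and the power figures also on an assumed effect. The dilution to two thirds under the three-visit arm effect needs only an effect equal at both follow-ups.

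**What to change.** Keep the repeated-measures framework and add, for LSAS:

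> Week-4 and week-8 LSAS will be compared between arms in a repeated-measures model with arm, visit, arm-by-visit and the screening-visit LSAS (not the earlier online eligibility LSAS) as covariate, in all randomised patients with available follow-up data. One primary contrast, [the arm difference averaged over weeks 4 and 8 / the arm difference at week 8], is named before unblinding and reported with its 95% CI.

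The sponsor keeps one of the two bracketed options. BDI should be analysed the same way with its own screening value: the current sentence is not limited to LSAS, and an LSAS-only replacement would remove the only analysis that could cover BDI. The response outcome (LSAS below 50), also labelled primary, needs a separate analysis, which this model does not supply. Covariance structure and degrees-of-freedom method are the statistician's choice.

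**Cost.** No new data and one degree of freedom (27 instead of 28). There is little or no gain if the correlation is low. The choice of contrast has a price either way. If the effect appears only at week 8 (no cut-off), the average has about 28/31/41% power against 58/67/83% for a week-8 contrast. If it appears only at week 4, the week-8 contrast has 5%.

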All procedures except photography and administration of investigational product will take place in the clinical offices of GWU MFA. For photography and administration of the investigational product, patients will be transported by taxi or private car service to the Chevy Chase Cosmetic Center, located at [name]. After the study procedures are complete, participants will be transported back to GWU MFA or to a nearby Metro station, if they prefer.

The injectable syringes will be prepared by [name] at the Chevy Chase Cosmetic Center. Syringes will contain either Botox or saline based on the randomization scheme. They will be marked with numbers written on tape affixed to clear envelopes that contain only the individual syringes. After being made, syringes will be stored in a refrigerator at 4 degrees Celsius in the Chevy Chase office. All patients will be examined and injected by a physician assistant, [name], who has been trained in the practice of injection, and was the injector for the Finzi and Rosenthal clinical trial studying Botox for the treatment of major depressive disorder. [name] will have no contact with patients, to maintain the blind.

The study medication or placebo will be injected into the procerus and corrugator supercilii frown muscles of each patient by a physician or physician's assistant.

Four and eight weeks following the injection, patients will be contacted and asked to complete the online LSAS and BDI self-assessments as well as reporting on concomitant medications and adverse events.

Participants will receive a gift card for up to \$45 at the completion of the study. They will receive \$25 if they complete the screening visit, and additional \$10 if they complete the first post-treatment online assessment, and another \$10 if they complete the second post-treatment online assessment.

Safety Measures

Adverse events will be collected via online assessments, and will be reviewed by the investigator within 24 hours. Patients will be contacted by telephone, or asked to come in for a face-to-face meeting if the investigator believes that the patient is at risk or if further evaluation of the adverse event is needed. Patients will be instructed to contact the investigator by telephone at any time if they have concerns about adverse events they may be experiencing.

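### The named repeated-measures ANOVA has no covariance assumption, sphericity correction or missing-form rule; a mixed model with screening LSAS as covariate would be safer

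*Combined protocol and SAP*

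**What the plan says.** The analysis is given in one sentence under Statistical Considerations in the Clinical Study Protocol Summary: "An ANOVA with repeated measures to determine whether there are statistical differences between the interventions will be used". The only other statement there is that power cannot be calculated. Nothing specifies which visits are levels of the repeated factor, which term carries the comparison, the covariance assumption, a sphericity correction, how the screening score enters, the analysis set, or what happens when a form is missing.

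The self-rated LSAS is collected "at screening, 4 weeks, and 8 weeks" (Primary Objective). Entry requires "A total score on the LSAS of 60 or greater" (Diagnosis and Criteria for Inclusion). Both follow-up scores are online self-reports: "Patients will be instructed to complete the LSAS and BDI online at week 4 and 8" (Duration of Treatment). The size is given as "Up to 100 subjects will be screened in order to enroll 30", and patients are "randomly assigned to the active group or control group in a 1:1 ratio", so about 15 per arm.

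**The concern.** Two properties of the classical method matter here.

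- **Sphericity.** With three visits, the within-patient F tests are valid without correction only if the three visit-to-visit differences have equal variance. One score is taken before treatment and two after it. If patients vary in their change, the week 4 to week 8 difference varies less than either difference from screening. The uncorrected arm-by-time p-value is then too small.
- **Complete rows.** The usual implementation drops any patient with a missing visit, so a patient who skips week 4 also loses an observed week-8 score. If non-completion is related to outcome, the remaining patients are a selected group.

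With 30 patients, neither a mild excess of false positives nor the loss of observed outcomes is easy to absorb. Because the plan is silent, the correction and the exclusions could be chosen after the data are seen.

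**Working it through.** **Inputs.** From the documents: 30 patients, 1:1 allocation (taken as 15 per arm), three LSAS time points, entry at 60 or more. The plan gives no alpha, SD, correlations or missing rate, so there is no figure of its own to reproduce. Assumed: two-sided 5%; underlying LSAS with mean 65 or 75 and SD 20; independent visit error with SD 8; a patient-specific pre-to-post change with SD c; 10% or 20% of forms missed.

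**Step 1: when sphericity fails.** Write screening = T + e0, week 4 = T + C + e1, week 8 = T + C + e2. The patient's level T cancels from every difference.

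- Variance of week 8 minus week 4: 2 × 64 = 128.
- Variance of either follow-up score minus screening: c² + 128.

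These agree only if c = 0. The two orthonormal contrasts have variances a = 64 and b = 64 + 2c²/3, and epsilon = (a + b)² / [2(a² + b²)]. For c = 15, b = 214 and epsilon = 278² / [2(4,096 + 45,796)] = 77,284 / 99,784 = 0.77. For c = 20, b = 330.7 and epsilon = 0.69. For c = 25, b = 480.7 and epsilon = 0.63.

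**Step 2: size of the uncorrected arm-by-time test.** Null trials with 15 per arm were simulated, 20,000 per setting:

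| Change SD c | Epsilon, with / without cut at 60 | Rejection with cut | Rejection without cut |
|---|---|---|---|
| 15 | 0.78 / 0.77 | 6.0–6.4% | 5.8–6.0% |
| 20 | 0.69 / 0.69 | 6.7–6.8% | 6.5–6.7% |
| 25 | 0.63 / 0.63 | 7.1–7.5% | 7.2–7.4% |

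With c = 0 and the cut acting alone, epsilon is 0.999 and rejection 5.1%. With c = 5 and the cut, rejection is 5.0%. The Greenhouse-Geisser correction returns the test to about 5%. The arm main effect, which needs no sphericity, rejects 4.7–5.3% throughout.

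**Step 3: ceiling.** With three visits epsilon cannot fall below 0.5. The worst case is P(F(1,28) > F0.95(2,56)) = 0.086.

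**Step 4: why the cut does not matter.** T cancels from the differences, so selection at 60 can act on them only through the screening error e0. It reduces the spread of the screening scores but barely alters the variances of the differences. A second set of runs, with SDs 20 to 28 and correlations 0.3 to 0.9, agrees. Equal correlations with the cut gave 4.9–5.1%. Unequal correlations or larger follow-up variance gave 5.3–7.1% with the cut and 5.4–7.2% without it.

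**Step 5: complete rows.** Let q be the proportion of each form missed, independently.

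| | Formula | q = 10% | q = 20% |
|---|---|---|---|
| Both forms | 30(1 − q)² | 24.3 | 19.2 |
| Week 8 observed | 30(1 − q) | 27.0 | 24.0 |
| At least one form | 30(1 − q²) | 29.7 | 28.8 |

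Patients dropped despite one completed form: 29.7 − 24.3 = 5.4, and 28.8 − 19.2 = 9.6. If the same patients miss both forms, 30(1 − q) = 27 or 24 are complete and no observed follow-up score is discarded.

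**Step 6: what that is worth.** Two-sample t-test at week 8, assumed difference 1.0 SD: power is 75% at 15 per arm, 70% at 13.5, 65% at 12 and 54% at 9.6. Under independent misses, deletion beyond the unavoidable loss therefore takes power from 70% to about 65% at q = 10% (24.3 complete, about 12 per arm), and from 65% to 54% at q = 20%.

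**The case against.** Much can be said for the plan, and several stronger readings do not survive.

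- **That the entry cut breaks sphericity.** A reader might infer this because screening scores are truncated and later ones are not. Sphericity concerns variances of differences, and steps 2 and 4 show the same result with and without the cut.
- **That the time tests definitely run above 5%.** The excess depends on a spread of patient change that the documents do not give, and it vanishes when that spread is small. The plan also does not say that screening is a level of the factor. With weeks 4 and 8 only, there are two levels and sphericity holds automatically. Nor are weeks 4 and 8 much closer in time: injection follows assessment by up to 7 days, so screening to week 4 is nominally 28 to 35 days against 28 days between the forms.
- **That the plan deletes patients who miss a form.** No such rule is written. It is the default of the classical method, and the wording could cover a mixed model.
- **That unsupervised forms make heavy loss likely.** The Study Design section says "patients will be contacted and asked to complete the online LSAS and BDI self-assessments" and pays $10 for each follow-up assessment. There is a window of ±7 days, and patients are selected as likely to adhere. The missing rates above are illustrations, and independent misses are the less favourable pattern.
- **That a Greenhouse-Geisser correction would suffice.** For sphericity alone it would. It does nothing about incomplete rows.

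What stands is that none of these benign readings is written down.

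**Conclusion.** The point holds as a weakness of the named method and its missing specification. In the classical three-visit form, the uncorrected arm-by-time test has a true size of about 5 to 7.5% under the assumed variances, with a ceiling of 8.6%. The test of the arm main effect keeps its size. Default deletion would discard an observed follow-up score for 5.4 (9.6) of 30 patients at 10% (20%) independent misses, and for none if misses coincide. All variances, alpha and missing rates are assumptions. The documents support neither blaming the LSAS threshold nor saying that patients will be deleted. The change should be made because it is cheap and the trial is small; the stated analysis is not shown to be invalid.

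**What to change.** Replace the ANOVA sentence with a mixed model for repeated measures on week-4 and week-8 LSAS. Terms: arm, visit, arm-by-visit, screening LSAS and screening LSAS-by-visit. Use an unstructured covariance and Kenward-Roger degrees of freedom. Include every randomised patient with at least one follow-up form. Report the arm difference at each visit with its 95% CI, and name one visit as the primary contrast. Add a missing-data sensitivity analysis, since the model relies on missingness being explained by observed scores. The LSAS is also completed before the visit ("Prior to screening, potential participants will fill out the LSAS and BDI online in order to determine initial eligibility"), so state which pre-treatment score is the covariate.

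The covariate should not be omitted. In the c = 15 setting, week-8 variance before selection is 400 + 225 + 64 = 689, screening variance is 400 + 64 = 464 and their covariance is 400. The variance left after adjustment is 689 − 400²/464 = 344. With the cut, follow-up SD is about 23 (variance 529), so leaving screening LSAS out would raise the variance of the arm difference by about 529/344 = 1.5 times.

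Cost: SAP wording, standard software and slightly more analysis work, with no new data. The p-value may be slightly less favourable than that of the uncorrected test.
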